### **Endpoint Visits:**

Few completed prospective trials have employed a treat and extend protocol. Therefore, there is little data regarding optimal endpoint usage. These endpoints will allow comparison of data from each cohort.

1. **Floating Endpoints** (also known as the Biological Endpoints): Analyses will be performed between weeks 24-28, between weeks 48-57, between weeks 72-82, week 104, between weeks 128-132 and week 156 (range to be determined by timing of last injection). If more than one possible endpoint exists, the time point closest to week 26, week 52, week 78, week 104, week 130 or week 156 will be used. This will be applied to both Cohort A and B, but likely to be most important for Cohort B. All endpoints are measured 4 weeks following the last injection.
2. **Hard Endpoints:** analyses will be performed at week 52 (day 365 $\pm$  7 days), week 104 (day 730  $\pm$  7 days) and week 156 (day 1095)

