#### **4.8 STATISTICAL METHODS**

##### **4.8.1 Analysis of the Conduct of the Study**

The analysis of data from week 52, week 104 and week 156 treatment period will be performed when all subjects have either completed the visit at week 52, week 104 and week 156 or discontinued early from the study.

The analysis of complete data (week 156) for the study will be performed when all subjects have either completed the visit at week 156 or discontinued early from the study, all data collected from the study are in the database, and the database is locked. Aggregate results of the week 52, week 104 and week 156 analysis, summarized by treatment group, may be reported to the public before completion of the study.

Descriptive summaries will include the mean, standard deviation, median, and range for continuous variables, counts and percentages for categorical variables.

Unless otherwise specified, all statistical tests are two sided. Detailed specifications of the statistical methods are described in the Statistical Analysis Plan.

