#### **4.8.3 Efficacy Analyses**

##### **Primary Outcome Measure**

The primary outcome measure for safety, tolerability and efficacy are:

- Mean change in ETDRS visual acuity from baseline to weeks 24-28, baseline to weeks 48-56, baseline to weeks 72-82, baseline to week 104, baseline to weeks 128-132 and baseline to week 156.

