#### **4.8.4 Missing Data**

Analyses of efficacy and safety will be based on available cases, without imputation for missing values.

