Auto Fluorescence	X	X	X	X	X	X	X	X	X	X	X	X	X	X
FP/ FA	X						X							X
CNVM	X						X							X
Measurement														
Study Drug Injection	X	X	X	X	X	X	X	X	X	X	X	X	X	X
Serum and/or Plasma Blood Draw														X

1. Injection administered on a PRN basis, if meets re-treatment criteria 2. Optional

Year 3 T-REX/PRN Treatment Schedule

Week (±7 days)	108	112	116	120	124	128	132	136	140	144	148	152	156
Visit	Visit	Visit	Visit	Visit	Visit	Visit	Visit	Visit	Visit	Visit	Visit	Visit	Visit
Vital Signs	30 X	31 X	32 X	33 X	34 X	35 X	36 X	37 X	38 X	39 X	40 X	41 X	42 X
Interval History (AE & Con Meds)	X	X	X	X	X	X	X	X	X	X	X	X	X
Indirect/Slit Lamp Exam	X	X	X	X	X	X	X	X	X	X	X	X	X
IOP (Pre & Post Injection)	X	X	X	X	X	X	X	X	X	X	X	X	X
Visual Acuity (ETDRS)	X	X	X	X	X	X	X	X	X	X	X	X	X
SD-OCT	X	X	X	X	X	X	X	X	X	X	X	X	X
Auto Fluorescence	X	X	X	X	X	X	X	X	X	X	X	X	X
Fundus Photo/ FA						X							X
CNVN Measurement						X							X
Study Drug Injection	X 												
Serum and/or plasma						X 							X 

1. Injection administered on a PRN basis, if meets re-treatment criteria      2. Optional

T-REX/Treat and Extend Arm/Cohort 2

		Week 12-156					
Week (±7 days)	Screen	Day0	Day7	4	8		
Visit	Visit	1	2	3	4	5	
Sign IFC	X						
Medical/Oph HX	X						
Vital Signs	X	X	X	X	X	X	
Interval History (AE & Con Meds)	X	X	X	X	X	X	
Indirect/Slit Lamp Exam	X	X	X	X	X	X	
IOP (Pre & Post Injection)	X	X	X	X	X	X	
Visual Acuity (ETDRS)	X	X	X	X	X	X	
SD-OCT	X	X	X	X	X	X	
Auto	X	X	X	X	X	X	
Fluorescence FP/FA	X						
CNVM Measurement	X						
Study Drug Injection 		X			X	X	
Plasma and/or Serum Sample 							

- Cohort 2 will receive 3 mandatory 0.5mg ranibizumab injections (Day 0, week 4, & week 8)
- Interval will remain at 4 weeks until there are no signs of exudative disease on SD-OCT or clinical examination
- Once a dry macula is achieved meaning there are no signs of exudative disease on SD-OCT or clinical examination the subject will start the Treat and Extend protocol, interval between injections is increased by 2-week intervals, starting at visit 6.
  - o Treatment Interval will not exceed > 12 weeks.
- If recurrent exudative disease is detected at any visit, after extension has been met, the interval between injections will decrease by 2 weeks (compared to the previous interval) until a "dry" macula is again established or subject is back at the 4-week interval.

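### The rule that floating endpoints fall 4 weeks after the last injection has no exception for eyes on PRN in year 3 and conflicts with the Year 3 PRN schedule; if followed, the weeks 128-132 primary acuity value depends on recent recurrence

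*Combined protocol and SAP*

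**What the plan says.** The primary outcome (sections 2.1, 3.4.1 and 4.8.3) is mean change in ETDRS acuity at six times, the last three being "baseline to week 104, baseline to weeks 128-132 and baseline to week 156". It does not say whether the floating or the hard value is meant.

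The Endpoint Visits text, given in sections 2.2, 3.4.2 and 4.8.3, applies the floating endpoints to both cohorts, names weeks 128-132 and week 156, and ends "All endpoints are measured 4 weeks following the last injection". It allows some movement ("range to be determined by timing of last injection") and, where several dates are possible, says "the time point closest to week 26, week 52, week 78, week 104, week 130 or week 156 will be used". The Appendix A notes for both arms also tie endpoint sessions to 4 weeks after an injection. Hard endpoints exist at weeks 52, 104 and 156 only.

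From week 104, section 3.2 puts all of Cohort A, and Cohort B eyes that are dry at the 12-week interval, on monthly visits with injection only when re-treatment criteria are met. Other Cohort B eyes continue treat-and-extend.

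The Appendix A table "Year 3 T-REX/PRN Treatment Schedule" schedules acuity at every visit, and fundus photography/angiography and lesion measurement at weeks 128 and 156. Its footnote "Injection administered on a PRN basis, if meets re-treatment criteria" attaches to the injection row, not to these measurements.

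Section 4.8.4: "Analyses of efficacy and safety will be based on available cases, without imputation for missing values". Section 4.8.1: "Detailed specifications of the statistical methods are described in the Statistical Analysis Plan". The supplied text contains no statement that settles the matter.

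**The concern.** The 4-week rule suits a regimen in which every eye is injected on a known schedule. Under PRN, an injection is itself a sign of recurrence. A rule requiring an injection exactly 4 weeks earlier then selects eyes on a post-baseline outcome, and the available-case rule leaves the others out. The eyes without a value would be those that did well enough not to need treatment.

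The Year 3 table suggests that PRN eyes were meant to be measured at fixed weeks. Angiography belongs to floating visits under section 4.5.1, and the table fixes it at weeks 128 and 156 whatever the injection history. But the Endpoint Visits text says otherwise. In an open-label trial, the choice between two conflicting instructions should not be left until the data can be seen.

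**Working it through.** The plan gives no figure to reproduce, so the check is a timeline count.

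**Inputs from the documents**
- PRN visits every 28 days (section 3.2), so nominal weeks 104, 108, ..., 156. The ±7-day tolerance is ignored.
- Cohort A: 20 subjects, last fixed injection at week 100 (sections 3.2 and 4.1.1). Section 2 says monthly for 104 weeks; the conclusion is the same either way.
- Floating times: weeks 128-132 and week 156.

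**Assumed:** probability p of re-treatment at a PRN visit, 0.2 to 0.5. The documents give no such rate.

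**Step 1. Which injections qualify.** A date 4 weeks after injection falls in weeks 128-132 only for injections at week 124 or 128 (124 + 4 = 128; 128 + 4 = 132). It falls at week 156 only for week 152. A Cohort A eye never re-injected after week 100 is 28 to 32 weeks past injection in the window and 56 weeks past at week 156, so it qualifies at neither.

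**Step 2. Share of PRN eyes with no value**

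| Time and reading | Formula | p = 0.2 | p = 0.5 |
|---|---|---|---|
| Weeks 128-132, independent visits | (1-p)² | 64% | 25% |
| Weeks 128-132, any dependence between visits | max(0, 1-2p) to 1-p | 60% to 80% | 0% to 50% |
| Week 156, floating value primary, only week 152 counts | 1-p | 80% | 50% |
| Week 156, floating value primary, date may move up to 8 weeks (injection at 144, 148 or 152; independent visits) | (1-p)³ | 51% | 12.5% |
| Week 156, hard value primary | none lost by this rule | 0% | 0% |

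The 8-week movement is illustrative. It is the distance a floating week-104 date would move for a 12-week Cohort B eye last injected at week 92: 92 + 4 = 96, and 104 - 96 = 8.

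If all 20 Cohort A subjects are still followed, 20 × [1-(1-p)²] = 7.2 to 15.0 have a weeks 128-132 value under independence.

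**Step 3. Unlimited movement.** A never re-injected Cohort A eye would supply the value from 100 + 4 = week 104 as its week-156 result. The eye is not lost, but its value is 52 weeks old.

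**Step 4. Effect on the mean.** With a share m missing, the available-case mean differs from the mean of all PRN eyes by m × (mean of qualifying eyes - mean of the others). At weeks 128-132 that is 0.64 to 0.25 letter per letter of difference. The difference is unknown in size and sign.

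**Step 5. Continuing treat-and-extend eyes.** For a fixed interval of k weeks and evenly spread phase, the share with no injection in weeks 124-128 (five whole weeks) is max(0, 1-5/k): 17% at k = 6, 38% at k = 8, 50% at k = 10, 55% at k = 11. These overlap the 25% to 64% for PRN eyes, though here the loss follows from visit phase rather than recurrence.

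**Step 6. Target and window.** The target week is 130 in the Endpoint Visits text, 132 in the visit-count secondary outcome and 128 in both Appendix A notes. Section 4.5.1 places angiography at weeks 124-128.

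**The case against.** A reader might infer that the trial discards dry eyes. The documents do not say so. No sentence excludes an eye, acuity is taken at all study visits (section 4.5.1), and the Year 3 table points towards fixed-week measurement. The loss follows only if the 4-week sentence is applied together with the available-case rule. That objection stands, and it makes this a conflict with a known consequence rather than a stated exclusion.

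A reader might also take the week-156 losses as the main result. They are conditional. The hard endpoint there is not tied to an injection, and the closest-date wording may let the floating date move.

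Third, a reader might infer that the comparison is tilted against one arm. All of Cohort A is on PRN while part of Cohort B is not, so the mechanisms differ. But Step 5 shows that continuing treat-and-extend eyes can miss the window about as often, and the mix of intervals in year 3 is unknown.

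Finally, the year-3 rationale asks whether eyes stay dry without injections, and OCT and injection counts address that directly. This is fair. But weeks 128-132 and week 156 are still listed in the primary acuity outcome, so the rule for obtaining those values has to work.

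What remains is that the 4-week sentence covers both cohorts and both year-3 times, has no PRN exception, and contradicts the Year 3 table.

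**Conclusion.** The concern holds in this form and should be fixed before the year-3 analysis. It is clearest at weeks 128-132, which have no hard endpoint: under the rule as written, 64% to 25% of PRN eyes would lack a primary value, assuming 20% to 50% re-treatment per visit, independent visits and the nominal schedule from week 104. At week 156 it arises only if the floating value is primary; then 80% to 50% have no value on the strict reading, or 51% to 12.5% if the date may move up to 8 weeks.

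The missing exception and the conflict between passages are certain from the text. The size rests on an assumed re-treatment rate. Neither the direction of bias nor a net imbalance between arms can be established from the documents. The choice between hard and floating values at week 104 is a separate trade-off and not part of this point.

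**What to change.** In the primary outcome of section 4.8.3, the Endpoint Visits text of sections 2.2, 3.4.2 and 4.8.3, and both Appendix A notes:

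1. State that the 4-week rule does not apply to eyes in the PRN phase. For those eyes the primary acuity value is the first scheduled PRN visit in weeks 128-132 (week 128 on the Year 3 table), and the week-156 visit (day 1095 ± 7, as in section 2.2), whatever the time since the last injection. With visits 4 weeks apart, a first visit in that window always exists, including for Cohort B eyes that switch to PRN after week 104 and before the window closes.
2. Use week 128 as the single target and weeks 128-132 as the single window. Align section 4.5.1 (Ocular Imaging), the visit-count secondary outcome and the Endpoint Visits text with them.
3. Keep the 4-week rule, within the window, for eyes still on treat-and-extend. Report by arm how many have no qualifying value, and do not label an out-of-window visit as weeks 128-132.
4. Tabulate time since last injection by arm at weeks 128-132 and 156.

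The cost is a few sentences and one table. The acuity is already collected, and no visit or treatment changes. The downside is that year-3 values will mix different times since injection, which the table makes visible.

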#### **4.8.4 Missing Data**

Analyses of efficacy and safety will be based on available cases, without imputation for missing values.

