### Ocular Assessments (All Study Visits)

- Best Corrected Visual Acuity Visual function of the study eye and the fellow eye will be assessed using the ETDRS protocol (The Early Treatment Diabetic Retinopathy Study Group, 1985) at 4 meters. (See Appendix F)
- IOP measurement of both eyes will be measured pre-dilation at every visit. IOP will be measured post intravitreal injection 30 min ( $\pm$  15 min) in the study eye. The method used for a subject must remain consistent throughout study.
- Slit lamp examination-Subject's anterior eye structure and ocular adnexa will be examined at each study visit using a slit lamp by the investigator.
- Indirect Ophthalmoscopy the subject's posterior pole and peripheral retina will be examined by indirect ophthalmoscopy at each study visit pre dose by the investigator
- Subjects will receive 0.5 mg intravitreal injection of ranibizumab per treatment schedule
- Telephone Safety Check 3 days ( $\pm$  1 day) post injection (after first injection only)

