#### **4.5.2 Early Termination Assessments**

Subjects who withdraw from the study prior to completion should return for an early termination evaluation 28 days ( $\pm$  7 days) following the last injection/study visit for monitoring of all adverse events (serious and nonserious). The schedule of assessments for early termination is the same as that for the final visit.

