#### **4.6 SUBJECT DISCONTINUATION**

Subjects have a right to withdraw from the study at any time.

The subject may be withdrawn from the study for any reason: if it is in the best interest of the subject, intercurrent illness, adverse events, or worsening condition. The Retina Consultants of Houston or [name], MD, may request the withdrawal of a subject because of protocol violations, administrative reasons, or any other valid and ethical reasons.

If a subject discontinues from the study, he or she will not be allowed to re-enter the study.

Reasons for subject discontinuation may include, but are not limited to, the following:

- Sensory rhegmatogenous retinal detachment or Stage 3 or 4 macular hole
- Investigator determination that it is not in the best interest of the subject to continue participation
- Pregnancy
- Need for anti-VEGF therapy other than ranibizumab in the study eye, unless as a part of the prospective investigational study design
- SAE
- Any other safety concerns

In the event of an adverse event in the study eye that is considered by the investigator to be severe in intensity, serious consideration should be given to discontinuing the subject from the study.

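### The available-case rule in section 4.8.4 may overstate later acuity gains if worse-seeing eyes leave; its effect on the cohort difference is of unknown sign, and a repeated-measures analysis would be a cheap improvement

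*Combined protocol and SAP*

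**What the plan says.** The missing-data rule is the single sentence of section 4.8.4: "Analyses of efficacy and safety will be based on available cases, without imputation for missing values". The primary outcome in section 4.8.3 is a series of changes from baseline, beginning "Mean change in ETDRS visual acuity from baseline to weeks 24-28, baseline to weeks 48-56, baseline to weeks 72-82, baseline to week 104" and continuing to week 156, six time points in all. Section 4.8.1 names descriptive summaries and two-sided tests and leaves detailed methods to a Statistical Analysis Plan. The combined document contains no separate text of that plan.

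Section 4.6 allows a subject to be withdrawn for any reason, giving as examples "if it is in the best interest of the subject, intercurrent illness, adverse events, or worsening condition". Its list of possible reasons includes an SAE and "Need for anti-VEGF therapy other than ranibizumab in the study eye". After a severe study-eye event, "serious consideration should be given to discontinuing the subject from the study". A subject who discontinues cannot re-enter.

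Acuity is well recorded before exit. Section 4.5.1 puts ETDRS testing at all study visits. Section 4.5.2 asks leavers to return 28 days (±7) after the last injection or study visit, and "The schedule of assessments for early termination is the same as that for the final visit".

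One provision works against loss of poor eyes. Section 3.2, under evidence of recurrent exudative activity, moves an eye with a loss of 20 letters or more to 4-weekly treatment. It does not withdraw the subject.

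**The concern.** On its natural reading, section 4.8.4 gives a mean at each time point in whoever is still present. That mean estimates the change in the randomised cohort only if leaving is unrelated to acuity. Several permitted reasons for leaving can be consequences of poor acuity, and treatment is open-label (section 4.2), so discretionary withdrawal is decided with the cohort known. The six time points could then describe progressively more selected sets of eyes.

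Two results are at stake. One is each cohort's reported mean gain, which is the primary outcome as written. The other is the difference between treat-and-extend and monthly dosing, from which readers will judge whether extension preserves vision. The acuity needed to reduce the problem is already collected, but the plan gives it no role after the subject has left.

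**Working it through.** **Inputs from the document.** 20 eyes in Cohort A (monthly) and 40 in Cohort B (treat-and-extend), section 4.1.1. The split agrees with 1:2 allocation of 60: 60/3 = 20 and 2 × 60/3 = 40. No alpha, power, SD, target difference, margin or dropout rate is given, so there is no planned precision to reproduce.

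**Assumed inputs.** Dropout, acuity gap, SD and correlation, as stated at each step.

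**Step 1: bias in one cohort's mean.** Let f be the fraction missing and g the shortfall of the missing eyes against the full cohort mean. The available-case mean is too high by f × g/(1 − f).
- 4 of 40 eyes missing, 15 letters worse: 0.10 × 15/0.90 = 1.67 letters.
- 2 of 20 eyes missing, 20 letters worse: 0.10 × 20/0.90 = 2.22 letters.

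**Step 2: bias in the difference, B minus A.** Let d be the fraction missing in a cohort and h the mean of stayers minus the mean of leavers. Each cohort's bias is d × h, so the difference is biased by dB × hB − dA × hA. With h from 10 to 20 letters in both cohorts:
- equal loss: 0;
- 20% missing in B and 10% in A: +1.0 to +2.0 letters (a B deficit is understated);
- 10% missing in B and 20% in A: −1.0 to −2.0 letters (a B deficit is overstated).

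**Step 3: simulation with one exit rule in both cohorts.** Week-104 SD about 12.4, mean gain 8 letters in A, visits every 4 weeks, exit possible after a change of −10 letters or worse, 200,000 eyes per cohort.

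| Exit chance per visit | True deficit in B | Available-case | Understated by |
|---|---|---|---|
| 10% | 3.03 | 2.60 | 0.43 |
| 10% | 5.03 | 4.29 | 0.74 |
| 30% | 3.05 | 2.35 | 0.70 |
| 30% | 4.93 | 3.69 | 1.24 |

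Between 7% and 13% left A, and between 10% and 21% left B.

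**Step 4: simulation in which exit may differ by cohort.** Six time points, SD 13, correlation 0.8 between neighbours, exit possible after a change of −5 letters or worse, 400,000 eyes per cohort. Entries in the last four columns are the deficit in B, in letters.

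| Exit (missing in A, B) | True | Available-case | Likelihood | Last value carried forward |
|---|---|---|---|---|
| Same rule (17%, 22%) | 3.03 | 2.53 | 3.04 | 3.15 |
| More from B (7%, 30%) | 3.00 | 0.12 | 2.97 | 5.00 |
| More from A (27%, 16%) | 2.93 | 4.43 | 2.94 | 1.36 |
| No deficit, same rule (17%, 17%) | 0.04 | 0.02 | 0.04 | 0.06 |

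In the last row both cohort means are about 2 letters too high, yet the difference is essentially unbiased.

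**Step 5: sampling error.** SE = SD × √(1/20 + 1/40) = 0.274 × SD. The 95% half-width, 1.96 × SE, is 5.4 letters at SD 10 and 8.1 at SD 15. At SD 12.4 the SE is 3.4, so the Step 3 biases are 0.43/3.4 = 0.13 to 1.24/3.4 = 0.37 of a standard error.

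**Step 6: does a model work at this size?** With 20 and 40 eyes, the Step 3 generating model, a 20% exit chance per visit and estimated covariance (random intercept and slope, 400 replicates), about 11% and 14% left. The average differences were −2.99 with full data, −2.45 with available cases and −3.08 with the mixed model. The available-case cohort means were 2.1 and 2.6 letters too high.

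**The case against.** A reader might infer that the rule necessarily biases later means upward and understates a treat-and-extend deficit. The document does not support that. Withdrawal under section 4.6 is discretionary, and the phrase about a worsening condition does not mention acuity. Section 3.2 keeps eyes with large losses on treatment, and smaller losses can shorten the interval or, in the PRN phase, prompt re-treatment. Steps 2 and 4 show that the contrast bias can be zero or reversed. Step 3 shows only understatement because it combines a true deficit in B with the same exit rule in both cohorts. This objection stands.

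A reader might also infer that leavers' acuity will certainly go unused. A likelihood model imputes nothing either, so the sentence does not forbid one, and section 4.8.1 defers detail. That stands as far as it goes. But no such model is named anywhere, and the only summaries described are simple ones.

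On size, a wider grid of assumed exit thresholds and probabilities gave 8% to 42% shrinkage of the deficit. That range describes the grid, not this trial, and I do not rely on it. The loss of 1.5 to 3 letters after reassignment from monthly to PRN dosing, cited in section 3.3, is another trial's result. The protocol does not adopt it as a margin.

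On the remedy, the simulations let exit depend only on recorded acuity, which favours the model. Steps 3 and 6 also assume 4-weekly visits in both cohorts, whereas Cohort B's intervals run up to 12 weeks and depend on disease activity. Pooling every visit would mix acuity taken at different times after injection. This stands and shapes the fix.

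**Conclusion.** The point holds as a cheap improvement. Section 4.8.4 sets a rule that is unbiased only if leaving is unrelated to acuity. Section 4.6 makes that doubtful without disproving it, and section 3.2 lowers the risk.

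If worse-seeing eyes leave, each cohort's later mean is too high, by about 1.7 to 2.2 letters at an assumed 10% loss of eyes 15 to 20 letters worse. The bias in the difference has unknown sign. It understates a treat-and-extend deficit if more, or worse-seeing, Cohort B eyes leave. It is zero if informative exit is equal, and it overstates the deficit if more Cohort A eyes leave.

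The contrast bias is 0.4 to 1.2 letters in Step 3 and reaches 2.9 (3.00 − 0.12) only under the strongly unequal exit of Step 4. All of these are below the 95% half-width of 5.4 to 8.1 letters, but they are systematic. Every size rests on assumed dropout, gap and SD.

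**What to change.** In section 4.8.4, for change in BCVA and in central foveal thickness:
- Analyse all randomised subjects by assigned cohort with a likelihood-based repeated-measures model. Use small-sample degrees of freedom and a covariance structure that 60 eyes can support. Report cohort means and differences at each time point.
- Use measurements comparable in both cohorts: the common early visits, the endpoint-window measurements taken 4 weeks after injection, and the early termination visit assigned to the next window. Model the hard endpoints separately.
- Keep available-case means as a descriptive or sensitivity table, and report withdrawals by cohort and reason.
- Add a delta-adjusted sensitivity analysis that sets later acuity, for eyes withdrawn for worsening or for another therapy, at for example 5, 10 and 15 letters below the model prediction.

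Carrying the last value forward is not a substitute: it missed the true difference whenever exit was unequal (Step 4).

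The cost is SAP wording and some programming, with no new visits, procedures or subjects. The downside is reliance on missing acuity being predictable from recorded acuity. That is weaker than what available cases require, and the delta adjustment tests departures from it.
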